## BACKGROUND

### 1) Discuss the following in paragraph format

- Discuss the importance of the topic (public health and/or clinical importance and impact on individuals/community; incidence, prevalence, mortality and morbidity)
- Critically appraise the relevant literature and discuss the state of current knowledge on the topic (including deficiencies in knowledge or gaps that make the study worth doing)
- Describe, in detail, your approach to address the research question
- Explain how your study will contribute to existing research and benefit other individuals or the wider community

**RESPONSE:** Mucolytics like n-acetylcystine have shown some success previously in the management of filamentary keratitis. There is no data evaluating whether Mucinex ® is also effective at decreasing severity. Anecdotally, patients have reported that filamentary keratitis symptoms improved with the use of mucinex ® for upper respiratory congestion. Filamentary keratitis is an uncommon (chronic) eye condition frequently associated with dry eye disease. Affected patients typically present with symptoms including foreign body sensation, grittiness, pain, photophobia, tearing and increased blink rate. On examination there are thread-like mucus filaments adherent to the corneal surface. Current management of filamentary keratitis addresses dry eye disease (lubrication, punctal plugs), inflammation (anti-inflammatory eye drops), mucous buildup (n-acetylcystine as a mucolytic) and filament removal with forceps. Previous histologic evaluation has demonstrated that the filaments consist of a corneal epithelial core wrapped in mucus. Staining has established that there is significant overlap in the mucins produced in the eye and those from the respiratory tract, most notably MUC5AC and MUC16. There are several proposed mechanisms for filament formation. The general process begins with an insult to the epithelium, Bowman's membrane, or both, and is commonly associated with some degree of aqueous tear deficiency. Primary treatment modalities include lubrication, filament removal, anti-inflammatories and mucolytics. Several past studies have shown limited success using n-acetylcystine for its mucolytic properties. To date there are no trials studying Mucinex ®, which is well-tolerated, cost-effective and has been shown to hydrate respiratory mucus secretions, in the treatment of filamentary keratitis.

## AIMS

2) Your aim(s) should arise from your literature review and state what the study hopes to accomplish.

**RESPONSE:** To determine the effectiveness of systemic mucinex ® in patients with filamentary keratitis.

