## OBJECTIVES

3) Your focused research question needs to be further refined into one or more study objectives. The study objective(s) should be single and quantifiable statement(s) that will allow you to answer your research question.

**RESPONSE:** To determine if the mucolytic properties of Mucinex ® are effective in reducing the amount of corneal filaments and improving symptomatology in patients with filamentary keratitis.

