## HYPOTHESES

**4a). Primary Hypothesis** - Hypotheses are more specific than objectives and amenable to statistical evaluation. Your primary hypothesis is your statement of the hypothesized effect on the primary outcome measure. A hypothesis is worded very simply and written as ‘testable’ statements. Your experimental results will prove or disprove your hypothesis. Hypotheses are generally stated in the null form ( $H_0$ ) as they have their basis in inferential statistics. Rejecting the null hypothesis increases our confidence, with a given level of probability, that there is a relationship between the variables being studied. However, a classic scientific hypothesis includes both a null and alternative ( $H_a$ ) hypothesis.

*\*e.g.  $H_0$ : Asthma prevalence rates are not different among children from low and high socioeconomic groups in Istanbul.  $H_a$ : Asthma prevalence rates are different among children from low and high socioeconomic groups in Istanbul.*

**RESPONSE:**  $H_0$ : Oral Mucinex ® does not reduce corneal filaments or symptomatology in patients with filamentary keratitis.  $H_a$ : Oral Mucinex ® twice a day reduces corneal filaments and the symptomatology in patients with filamentary keratitis.

**4b). Secondary Hypotheses** - Although a study is usually based around a primary hypothesis, secondary hypotheses may also be pre-specified although based on outcomes of lesser importance or additional interest. As the primary hypothesis is usually the basis for statistical power calculations, secondary hypotheses with insufficient power will generally not lead to statistically robust conclusions.

**RESPONSE:** N/A

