## STUDY DESIGN

**5)** State the design of the research (e.g. randomized controlled study, cross-sectional survey, prospective or retrospective cohort/case-control).

*\*Whatever the study design, you need to ensure that you provide the reader with a clear statement and description of your proposed design. You may also explain why the particular study design has been chosen in preference to other possible designs (i.e. justification for choice of study design)*

**RESPONSE:** Prospective, non-randomized, non-controlled study.

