## ELIGIBILITY CRITERIA

**6a). Inclusion Criteria** - Inclusion criteria are the ‘characteristics’ that clearly describe the study population that are required for a subject to be included in the study. The criteria may be based on factors such as age, gender, the type and stage of a disease, previous treatment history, and co-morbid medical conditions. They may state appropriate criteria for admitting special ‘at-risk’ populations such as women of reproductive age, children or patients with disease states or organ impairment.

**RESPONSE:** 1) Patients 18 years or older who have filamentary keratitis in at least one eye. 2) Schirmers test  $\geq 3$ mm in the eye diagnosed with filamentary keratitis (can be one eye or both the eyes).

**6b. Exclusion Criteria** - Provide details of participants that will be considered ineligible to participate and justification for their exclusion. These criteria are not always clinical in nature, aiming principally to accommodate participants in a safe and ethical manner. Criteria may include circumstances that interfere with the participant's ability to give informed consent (diminished understanding or comprehension, or a language other than English spoken and an interpreter unavailable), contraindications to the study treatment(s)/procedure(s), taking certain concomitant medication(s), or conditions that interfere with a patient's ability to comply with all treatment(s)/procedure(s).

**RESPONSE:** 1) Less than 18 years or older than 80 years of age; 2) Patients unable to provide informed consent; 3) Patients unable to attend a follow-up visit within 4 ( $\pm 1$ ) weeks; 4) Active ocular surface infection of any type; 5) Recent ocular surgery ( $< 30$  days); 6) History of nephrolithiasis as Mucinex ® has been associated in rare cases to the development of kidney stones; 7) Schirmer test  $< 3$ mm (in study eye; can be one eye or both the eyes); 8) History of hypersensitivity to Mucinex ®; 9) Concurrent eye disease requiring immediate initiation of a new treatment (e.g., topical steroids); 10) Restrictions for water intake can exacerbate the risk of nephrolithiasis and thus patients taking oral Mucinex ® are instructed to take each dose with a generous amount of water.

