## STUDY PROCEDURES

**8)** In this section you need to clearly and comprehensively describe exactly what will happen to participants once they are enrolled in your study. Depending on the study it might include how potential participants will be approached, when they will be randomized, the frequency and duration of visits or whether they are expected to self-complete a daily diary at home, the duration of the study or follow-up, and any measurements taken at each visit (e.g. questionnaires, physical measurements, biological samples).

You should include precise details of the treatment(s)/intervention(s) intended for each group/participant. You should also provide details of any follow-up schedule (i.e. time between visits) and consider how you will monitor participants' adherence with the treatment schedule. You might also describe under which circumstances participants may be withdrawn and how this will occur. A schematic diagram or flow chart may be useful for this section.

**RESPONSE:** To test the hypothesis that Mucinex® administration will reduce the signs and symptoms of filamentary keratitis, patients with the diagnosis of filamentary keratitis will be enrolled. At the initial visit (Day #1), visual acuity, number of filaments on the cornea, schirmers test, ocular surface symptoms, these are standard, non-invasive common clinic procedures that will be recorded. The patient will then be instructed to continue their current medication regimen, with no alterations. The patient will then be given 600mg tablets of extended-release Mucinex® to take home, and will be instructed to take them twice a day with abundant water until the next visit in 4 weeks. If patient misses a dose, they are not required to make up for missed dose and can continue to take the next dose. At the follow up visit the visual acuity, number of filaments on the cornea, and ocular surface symptoms will be assessed.

The investigators will screen the patients for a history of nephrolithiasis, a contraindication of this therapy prior to their enrollment. Patients will continue their usual eye treatment regimen while participating in this study.

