### RESPONSE:

This will be a first-of-its-kind study evaluating an FDA approved and over-the-counter available drug (guaifenesin; Mucinex®) to treat cough as part of the symptoms of common cold. Our study will be the first to evaluate the effect of Mucinex® alleviating the symptoms of filamentary keratitis. No data are available to estimate the changes expected after initiation of Mucinex®. This is a pilot study and represents minimal to no risk to participants, and involves no additional procedures other than the routinely performed clinical assessments. In this pilot study we aim to enroll 15 participants.

**14) Statistical methods** - The statistical methods used for the study objectives/hypotheses (e.g. t-test, chi-squared, multivariate modeling) must be sufficiently detailed. If conducting a randomized controlled study, you should state whether methods will include an “intention to treat” (ITT) analysis, per protocol analysis, or both. An ITT analysis is preferred as it compares all subjects in the groups to which they were originally randomly assigned (despite withdrawal, treatment failure or cross-over). Consultation with a statistician is strongly recommended. [See Harvard Catalyst Statistical Consulting for more information.](#)

**RESPONSE:** We will use a paired T test or a Wilcoxon signed-rank test, depending on the distribution of the data, to assess whether there is a significant difference between pre- and post-therapy symptoms of filamentary keratitis.

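### The aim and hypotheses ask whether Mucinex works, but the uncontrolled paired test shows only change from baseline, and the all-patient result includes patients whose topical steroids were increased at the same time

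*Protocol*

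**What the plan says.** **The question.** The Protocol's Aims section reads "To determine the effectiveness of systemic mucinex". Its Objectives section asks whether the drug's mucolytic properties "are effective in reducing the amount of corneal filaments and improving symptomatology in patients with filamentary keratitis". The null hypothesis under Hypotheses (4a) is that oral Mucinex "does not reduce corneal filaments or symptomatology in patients with filamentary keratitis", and the alternative is that it does reduce them. All of these concern an effect of the drug.

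**The design and test.** Study Design (5) states: "Prospective, non-randomized, non-controlled study". Protocol item 14 and the SAP's Statistical Test of Hypothesis both give a paired t-test or a Wilcoxon signed-rank test, chosen by distribution, comparing baseline with follow-up. The SAP sets two-sided significance at 0.05. On expected change, Protocol item 13 says "No data are available to estimate the changes expected after initiation of" Mucinex, and it calls the study a pilot aiming for 15 participants.

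**Background treatment.** Study Procedures (8) has patients "continue their current medication regimen, with no alterations". Exclusion 9 bars "Concurrent eye disease requiring immediate initiation of a new treatment (e.g., topical steroids").

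**The analysis sets.** In SAP Figs. 2 and 3, panel A covers all patients who received guaifenesin. Panel B separates those whose only new treatment at baseline was guaifenesin from those who also had a simultaneous increase in topical corticosteroids. The protocol mentions no such split.

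**The concern.** A paired test cannot tell a drug effect from anything else that moves scores over four weeks, such as natural course, regression to the mean or another treatment started on the same day. Two features of the protocol partly support reading change as a drug effect. The disease is described as chronic ("Filamentary keratitis is an uncommon (chronic) eye condition frequently associated with dry eye disease"), and other treatment was to stay fixed. The first is untested here, and the second did not hold for all patients.

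This matters in two ways. If the all-patient panels carry the message, any steroid effect is counted as a guaifenesin effect. If no set is named as the basis for the claim, whichever of two results looks better can be cited after both have been seen.

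**Working it through.** The documents give no effect size, SD or power, so there is no stated figure to reproduce. The number analysed does not appear in the text available either. The figures below are therefore illustrations. Every input is assumed, including n = 15, which is the enrolment target. Changes are normal and in units of the SD of within-patient change, with positive meaning improvement.

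**Step 1: what each set estimates.** Let g be the guaifenesin effect, s the steroid effect, u the improvement unrelated to either (drift), and k the number of n patients with a steroid increase.

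- All patients: mean change = g + (k/n)s + u
- Guaifenesin-only: mean change = g + u

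The subset removes s. Neither set removes u.

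**Step 2: steroid effect in the pooled test (g = 0, u = 0, n = 15).** The shift in the pooled mean is (k/15)s. The probability of a significant improvement (upper tail of the two-sided 0.05 t-test) comes from simulation.

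| k | s | Pooled shift | Pooled test | Guaifenesin-only test |
|---|---|---|---|---|
| 3 | 0.5 to 1.0 | 0.10 to 0.20 | 5.1% to 8.3% | 2.5% |
| 5 | 0.5 to 1.0 | 0.17 to 0.33 | 7.9% to 16.8% | 2.5% |
| 7 | 0.5 to 1.0 | 0.23 to 0.47 | 11.9% to 30.3% | 2.5% |

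**Step 3: drift (g = 0, s = 0).** The probability of a significant improvement is P(T > t(0.975, n−1)), where T is noncentral t with n−1 degrees of freedom and noncentrality u√n. For n = 15 and u = 0.3, the noncentrality is 0.3 × 3.873 = 1.16 and the critical value is 2.145, which gives 19.0%.

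| n | u = 0 | u = 0.1 | u = 0.2 | u = 0.3 |
|---|---|---|---|---|
| 15 | 2.5% | 5.5% | 10.8% | 19.0% |
| 12 | 2.5% | 5.0% | 9.3% | 15.6% |
| 10 | 2.5% | 4.7% | 8.2% | 13.4% |
| 8 | 2.5% | 4.3% | 7.1% | 11.1% |

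The subset's rates are lower only because it is smaller. Its bias from drift is the same.

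**Step 4: no governing set.** If significance in either set could be claimed and nothing changes at all, the simulated two-sided error is about 7% with 12 guaifenesin-only patients and about 9% with 5, against the nominal 5%.

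**Step 5: is the subset conservative?** Suppose steroids were increased in patients who were worse on Day 1. Those removed are then the patients most likely to regress towards better scores. The simulation takes score reliability of 0.9 or 0.7, removes the 3, 5 or 7 highest of 15 on a variable correlated 0.3, 0.5 or 1.0 with the Day 1 score, and sets drug and steroid effects to zero.

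- No drift: false improvement about 0.4% to 2%, false worsening about 3% to 11%.
- Drift 0.2 SD: false improvement about 2% to 8%.
- Drift 0.3 SD: false improvement about 3% to 14%.

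The net direction depends on how much drift there is, which is unknown.

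**Step 6: precision.** The 95% confidence interval half-width is t(0.975, n−1)/√n. At n = 15 this is 2.145/3.873 = 0.55 SD. It is 0.64, 0.72 and 0.84 SD at n = 12, 10 and 8.

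**The case against.** **The design is disclosed.** The protocol says the study is uncontrolled and a pilot. The SAP describes its analysis as change over time, and its captions are temporal rather than causal. That is fair: nothing is hidden, and neither document states a causal conclusion. But the aim and hypotheses are causal, they are tested at 0.05, and neither document limits what a significant result may be taken to mean.

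**Naming the subset is itself post hoc.** The protocol foresaw one set of all participants, which panel A matches, so reporting both sets with equal prominence might seem enough. The post hoc point stands and must be declared. Equal prominence is not enough, because a pooled result containing a known second treatment change cannot support a statement about guaifenesin alone.

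**Some gaps may be artefacts.** The figures are not shown in the version reviewed. A reader might infer that group sizes were never reported. The documents do not support this, since the panels may show them. Any limitation stated in the journal article is also out of view.

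**Exclusion 9.** A reader might infer that the steroid patients were ineligible. The text does not establish this. The criterion concerns concurrent eye disease needing a new treatment, whereas the captions describe an increase. The firm inconsistency is between Study Procedures and the captions.

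**Conclusion.** The point holds. The test addresses change from baseline, not an effect of Mucinex. The instruction to leave the regimen unaltered, which was the main support for a causal reading, was not kept for all patients, and nothing in the text available says which analysis set carries a statement about guaifenesin.

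The actual bias cannot be computed. Under the assumed inputs, the pooled test credits guaifenesin falsely in 5% to 8%, 8% to 17% or 12% to 30% of trials with 3, 5 or 7 steroid patients. Drift of 0.1 to 0.3 SD alone gives 5.5% to 19.0% at n = 15, and moving to the subset does not cure it.

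A reader might infer that the guaifenesin-only set errs on the safe side because sicker patients were removed. That holds only with no drift. With 0.3 SD of drift, false improvement exceeds 2.5% throughout the range examined, so the subset should not be presented as conservative. Nor does this point show that the reported change is wrong, only that it cannot be attributed to the drug.

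**What to change.** 1. **Reconcile the passages.** Study Procedures (8) and the SAP captions to Figs. 2 and 3 must be brought into agreement, and the scope of exclusion 9 clarified. Report the steroid increases as a departure from the stated procedure. No view is taken here on which clinical rule is right.
2. **Name the set.** Base any statement about guaifenesin on the guaifenesin-only patients already separated in panels 2B/3B. Show the all-patient result beside it, labelled as change on guaifenesin with or without a steroid increase. State that this choice was made post hoc, and give the number in each set if the figures do not already show it.
3. **Reword the conclusion.** Report within-patient change over 4 weeks while taking guaifenesin, with an estimate and 95% confidence interval. Say that the uncontrolled design cannot attribute the change to the drug. The SAP is dated 2019 and describes a completed analysis, so leave the hypotheses as filed and add the qualification openly.

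**Cost.** No new patients or visits are needed, only some wording and a small added analysis for the interval. The subset's interval is wider (half-widths in Step 6). The subset is also non-random and the net direction of its bias is unknown, which the report should say.

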## OBJECTIVES

3) Your focused research question needs to be further refined into one or more study objectives. The study objective(s) should be single and quantifiable statement(s) that will allow you to answer your research question.

**RESPONSE:** To determine if the mucolytic properties of Mucinex ® are effective in reducing the amount of corneal filaments and improving symptomatology in patients with filamentary keratitis.

## HYPOTHESES

**4a). Primary Hypothesis** - Hypotheses are more specific than objectives and amenable to statistical evaluation. Your primary hypothesis is your statement of the hypothesized effect on the primary outcome measure. A hypothesis is worded very simply and written as ‘testable’ statements. Your experimental results will prove or disprove your hypothesis. Hypotheses are generally stated in the null form ( $H_0$ ) as they have their basis in inferential statistics. Rejecting the null hypothesis increases our confidence, with a given level of probability, that there is a relationship between the variables being studied. However, a classic scientific hypothesis includes both a null and alternative ( $H_a$ ) hypothesis.

*\*e.g.  $H_0$ : Asthma prevalence rates are not different among children from low and high socioeconomic groups in Istanbul.  $H_a$ : Asthma prevalence rates are different among children from low and high socioeconomic groups in Istanbul.*

**RESPONSE:**  $H_0$ : Oral Mucinex ® does not reduce corneal filaments or symptomatology in patients with filamentary keratitis.  $H_a$ : Oral Mucinex ® twice a day reduces corneal filaments and the symptomatology in patients with filamentary keratitis.

**4b). Secondary Hypotheses** - Although a study is usually based around a primary hypothesis, secondary hypotheses may also be pre-specified although based on outcomes of lesser importance or additional interest. As the primary hypothesis is usually the basis for statistical power calculations, secondary hypotheses with insufficient power will generally not lead to statistically robust conclusions.

**RESPONSE:** N/A

## STUDY DESIGN

**5)** State the design of the research (e.g. randomized controlled study, cross-sectional survey, prospective or retrospective cohort/case-control).

*\*Whatever the study design, you need to ensure that you provide the reader with a clear statement and description of your proposed design. You may also explain why the particular study design has been chosen in preference to other possible designs (i.e. justification for choice of study design)*

**RESPONSE:** Prospective, non-randomized, non-controlled study.

## ELIGIBILITY CRITERIA

**6a). Inclusion Criteria** - Inclusion criteria are the ‘characteristics’ that clearly describe the study population that are required for a subject to be included in the study. The criteria may be based on factors such as age, gender, the type and stage of a disease, previous treatment history, and co-morbid medical conditions. They may state appropriate criteria for admitting special ‘at-risk’ populations such as women of reproductive age, children or patients with disease states or organ impairment.

**RESPONSE:** 1) Patients 18 years or older who have filamentary keratitis in at least one eye. 2) Schirmers test  $\geq 3$ mm in the eye diagnosed with filamentary keratitis (can be one eye or both the eyes).

**6b. Exclusion Criteria** - Provide details of participants that will be considered ineligible to participate and justification for their exclusion. These criteria are not always clinical in nature, aiming principally to accommodate participants in a safe and ethical manner. Criteria may include circumstances that interfere with the participant's ability to give informed consent (diminished understanding or comprehension, or a language other than English spoken and an interpreter unavailable), contraindications to the study treatment(s)/procedure(s), taking certain concomitant medication(s), or conditions that interfere with a patient's ability to comply with all treatment(s)/procedure(s).

**RESPONSE:** 1) Less than 18 years or older than 80 years of age; 2) Patients unable to provide informed consent; 3) Patients unable to attend a follow-up visit within 4 ( $\pm 1$ ) weeks; 4) Active ocular surface infection of any type; 5) Recent ocular surgery ( $< 30$  days); 6) History of nephrolithiasis as Mucinex ® has been associated in rare cases to the development of kidney stones; 7) Schirmer test  $< 3$ mm (in study eye; can be one eye or both the eyes); 8) History of hypersensitivity to Mucinex ®; 9) Concurrent eye disease requiring immediate initiation of a new treatment (e.g., topical steroids); 10) Restrictions for water intake can exacerbate the risk of nephrolithiasis and thus patients taking oral Mucinex ® are instructed to take each dose with a generous amount of water.

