## STUDY OUTCOMES

**7a). Primary Outcome** - The primary outcome should be the most important and clinically relevant outcome (e.g. clinical, psychological, economic, or other) of the study. This is the measure used to answer your study aim. However, it is also the outcome used to calculate study sample size and power and test the primary research hypothesis. Generally, no more than 1-2 primary outcome measures are pre-specified. Primary outcome measures may be measured in various ways such as: binary (e.g. caesarean/no caesarean, blood loss  $\geq 500$ mL/blood loss  $< 500$ mL); continuous (e.g. weight - kg, blood loss - mL); ordinal (e.g. pain - mild, moderate, severe); time to event (e.g. survival), and counts (e.g. number of infections, number of events occurring).

**RESPONSE:** Reduction of symptoms according to the Ocular Surface Disease Index score after treatment with oral mucinex ® twice a day (total dose is 1.2 g/day) for 4 weeks

**7b). Secondary Outcome(s)** - Secondary outcome(s) are measures of additional or less important research interest. They may include additional clinical, psychological, economic, or safety outcomes (e.g. treatment related side effects/adverse events). However, as these endpoints are not used to calculate study power and sample size it is often not possible to draw robust conclusions from the results.

**RESPONSE:** Reduction in the number of corneal filaments after treatment with oral Mucinex ® twice a day (total dose is 1.2 g/day) for 4 weeks.

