## Statistical Test of Hypothesis

We calculated the difference in the mean number of filaments and OSDI score between baseline and follow-up visits and evaluated their change over time. We used the paired-sample Wilcoxon signed-rank test if data did not follow a normal distribution and the paired Student t-test in the case of normally distributed data. For all the analyses we considered the average value of both eyes for all variables with the exception of symptom scores (OSDI), which were considered per patient. Data are presented as the mean  $\pm$  standard deviation (SD), a range for continuous variables, and percentages for categorical variables. A twotail P value of less than 0.05 was considered statistically significant in all statistical tests. The statistical analysis was performed using STATA 13.0 (StataCorp, College Station, TX).

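### The SAP averages filament counts over both eyes, although patients may have disease in one eye only and the Schirmer limit is set eye by eye

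*Protocol*

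**What the plan says.** **Eligibility (protocol, 6a and 6b).** Inclusion 1 admits adults "who have filamentary keratitis in at least one eye", so unilateral and bilateral disease both qualify. Inclusion 2 requires a Schirmer value of at least 3 mm "in the eye diagnosed with filamentary keratitis (can be one eye or both the eyes". Exclusion 7 removes patients with a value below 3 mm, qualified by "in study eye; can be one eye or both the eyes". The protocol does not define 'study eye' and gives no rule for a patient with two affected eyes on opposite sides of 3 mm.

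**Outcomes (protocol, 7a and 7b).** The primary outcome is "Reduction of symptoms according to the Ocular Surface Disease Index score after treatment". The secondary outcome is "Reduction in the number of corneal filaments after treatment with oral Mucinex". The primary hypothesis (4a) names both filaments and symptoms.

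**Analysis (SAP, Statistical Test of Hypothesis).** The stated rule is "For all the analyses we considered the average value of both eyes for all variables", and its only exception is OSDI: "with the exception of symptom scores (OSDI), which were considered per patient". The average is not limited to affected, eligible or study eyes.

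**The concern.** The protocol defines disease and tear production at the level of the eye, but the SAP drops that distinction when it forms the filament outcome. Two kinds of eye outside the eligibility definition can enter the average:

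- the unaffected fellow eye of a unilateral patient;
- an affected eye below the Schirmer limit, if a patient with discordant eyes was enrolled.

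The first does not depend on any ambiguity, because inclusion 1 plainly allows one affected eye. The reported mean change, its SD and the paired test would then reflect the mix of unilateral and bilateral patients as well as the response to treatment. With a target of 15 participants, a few patients can shift the result. Filament count is the study's measured sign of the disease and part of the hypothesis it sets out to test, so a reader needs to know which eyes it describes.

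**Working it through.** The plan states no figure to reproduce. Item 13 of the protocol gives a target of 15 with no expected change or SD. What can be checked is what the averaging rule does, and how the two Schirmer criteria treat a patient with discordant eyes.

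**1. Unilateral patients.** Inputs: n = 15 (protocol, item 13) and the averaging rule (SAP). Assumptions: every affected eye changes by the same amount d; unaffected eyes have zero filaments at both visits; u patients are unilateral (the number is not given).

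A unilateral patient contributes (d + 0)/2 = d/2. A bilateral patient contributes (d + d)/2 = d.

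Reported mean = [u × d/2 + (15 − u) × d]/15 = d × (1 − u/30)

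| u | reported mean ÷ affected-eye change |
|---|---|
| 0 | 1.00 |
| 5 | 1 − 5/30 = 0.83 |
| 10 | 1 − 10/30 = 0.67 |
| 15 | 1 − 15/30 = 0.50 |

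**2. Effect on the test.** At u = 15 every difference is halved. Mean and SD halve together, so the paired t statistic is unchanged; the ranks and signs are unchanged, so the Wilcoxon result is too. In a mixed sample, unilateral patients enter at half scale. At u = 5 the mean is 5d/6, and the sum of squares about it is 5 × (d/2 − 5d/6)² + 10 × (d − 5d/6)² = 5d²/9 + 10d²/36 = 0.833d². The SD is √(0.833/14) × d = 0.244d. This spread comes from laterality alone, since every affected eye was assumed to change equally.

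**3. Discordant Schirmer values.** Take a bilateral patient with one eye at or above 3 mm and one below.

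| reading | inclusion 2 | exclusion 7 | enrolled |
|---|---|---|---|
| (a) one eye is enough in each criterion | met | met | no, if the exclusion prevails |
| (b) every affected eye must pass, and any failing eye excludes | not met | met | no |
| (c) one eye is enough for inclusion, and 'study eye' means the qualifying eye | met | not met | yes |
| (d) all eyes are required in each criterion | not met | not met | no |

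The wording does not select one of these. If such a patient is enrolled and the second eye changes by r times the eligible eye's change, the patient's value is (1 + r)/2 of the eligible-eye change: 0.50 at r = 0, 0.75 at r = 0.5, 1.00 at r = 1 and 1.25 at r = 1.5.

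With k such patients among 15, and all others contributing the full change, the mean is multiplied by [(15 − k) + k(1 + r)/2]/15:

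| k (assumed) | r = 0 | r = 1 | r = 1.5 |
|---|---|---|---|
| 1 | 0.967 | 1.000 | 1.017 |
| 3 | 0.900 | 1.000 | 1.050 |
| 5 | 0.833 | 1.000 | 1.083 |

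**The case against.** Averaging two eyes is a respectable choice. It gives one value per patient and avoids treating correlated eyes as independent. The drug is oral, so both eyes are exposed, and total filament burden per patient is a legitimate target. Much of the unilateral effect is rescaling: a fall from 10 to 4 becomes 5 to 2, which is 60% either way. Filament count is secondary, and the primary outcome is exempt from averaging. The analysts may also have used only the affected eye in unilateral patients.

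Part of this stands. One value per patient should be kept, and the all-unilateral case leaves the tests unchanged. It does not rescue the rule in a mixed sample, where unilateral patients are scaled differently from bilateral ones. The SAP neither argues for a two-eye burden nor records an affected-eye exception.

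Two stronger readings are tempting:

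- **That a discordant patient meets both inclusion 2 and exclusion 7.** This is one of four readings. Even there, a met exclusion would normally bar enrolment, so the eye below the limit would not reach the analysis. The documents support only that 'study eye' and the rule for discordant eyes are undefined.
- **That the filament effect is cut in half.** For a discordant patient this needs no response at all in the second eye. For the whole sample it needs every patient to be unilateral, which is the case where the tests do not change.

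**Conclusion.** The concern holds for the filament outcome. As written, the SAP averages in unaffected fellow eyes, and it would also average in an affected eye below 3 mm wherever eligibility was read to admit that patient. Under equal change per affected eye and zero counts in fellow eyes, the reported mean change is 0.83 of the affected-eye change with 5 unilateral patients of 15, and 0.67 with 10. For discordant patients the direction is open, since it depends on how the second eye responds. The documents give neither number of patients, so the actual effect cannot be fixed.

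The OSDI score is taken per patient, so the calculation of the primary outcome is untouched; only a change in who is enrolled could reach it. The undefined 'study eye' is a missing detail to be reconciled. The averaging rule is a stated choice that can be improved at little cost.

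**What to change.** **SAP.** For filament count, replace the both-eye average with the average over eyes that had filamentary keratitis at baseline and met the protocol's Schirmer criterion, one value per patient. Keep the both-eye average as a sensitivity analysis; it also covers filaments that appear in a fellow eye during follow-up. Report how many patients were unilateral, bilateral, and bilateral with discordant Schirmer values.

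**Protocol.** Reconcile inclusion 2 with exclusion 7 through one definition of 'study eye' and an explicit rule for discordant eyes. That rule is for the investigators to set; this review does not propose one.

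**Cost.** The SAP is written in the past tense, so this means a short re-analysis as well as a changed sentence. Some patients would contribute one eye instead of two. No new measurements should be needed, but that rests on counts having been recorded by eye, which the averaging implies and the documents do not state.
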